- **Sample size justification:** There has been no study evaluating the accuracy of canine retraction with this software. This will be a pilot study from which preliminary data will be obtained for a larger study.

- **Method of data gathering:** Patients undergoing orthodontic treatment in the Center for Orthodontic Care at UConn Health will be evaluated for the inclusion criteria. A total of twenty patients whose orthodontic treatment plan required extraction of at least one premolar in the maxillary arch will be recruited. The patient will be required to take photographs and video scans as dictated by Dental Monitoring (DM) on the first and final days of the study period (five weeks), while iTero scans are taken by the provider in clinic on these same days. The patients will also be asked to take photograph and video DM scans every 4 days during the 5-6 weeks period. DM will provide cheek retractors and scan boxes, which are FDA approved, and the patient will be instructed on how to use the devices to procure photographs and videos.
- **Method of measuring accuracy:** Compare the DM scans taken by the patient to iTero digital scans taken by the provider. This can be done by superimposing the stereolithographic (STL) files created from each scan and assessing the amount of deviation between the 3D models.
- **Method of measuring tooth movement:** Quantify the types of tooth movement occurring during canine retraction in buccolingual, mesiodistal, and incisogingival planes using Doctor Dashboard software available in DM. DM's 3D matching technology allows superimposition of teeth from each 3D model created per scan. Each tooth and its movements are graphed in a detailed manner to provide precise information about its type of movement.
- **Confidentiality of data/privacy of subjects:** Each subject will be assigned a code; the correlation will be denoted in a master list, which will be kept in a locked file cabinet, only accessible to the study coordinator and principal investigator.

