Only after Consent and HIPAA Forms have been signed, the PI, co-investigator and/or study coordinator will confirm eligibility and complete the Screening Form. Once eligibility criteria have been met, the patient and/or parent will be informed. If the patient meets the inclusion criteria and would like to participate in the study, they will sign the HIPAA form and will be protected under HIPAA. If the patient meets the inclusion criteria and does not want to participate, electronic identifiers will be deleted and paper identifiers will be shredded as soon as patient decides not to participate. If the patient does not meet the inclusion criteria, electronic identifiers will be deleted and paper identifiers will be shredded as soon as the patient is deemed not a candidate for the study.

- **Study Procedure:** The study coordinator will approach patients undergoing space closure as per their premolar extraction treatment plan at the Division of Orthodontics at the

University of Connecticut. If the patient fulfills inclusion/exclusion criteria and consents to participate in the study, the study coordinator will take a digital scan using iTero Element 2 in the clinic the same day if possible, marking day 1 of the study. Then, the patient will be instructed to download the Dental Monitoring app on his/her smartphone and will be provided with all accompanying tools and education to successfully take photo and video scans themselves the same day in the orthodontic clinic. The DM cheek retractor and scan box will be provided to the patient to take home for data procurement. The cheek retractor and scan box are similar to the devices/instruments used at regular orthodontic appointments and are of minimal risk to the patient. They are used to separate the patient's soft tissue to allow good visual access of the patient's intraoral structures. At the patient's subsequent 5-6 weeks follow up appointment, another in-office iTero digital scan will be taken, marking the final day of the study. Another DM scan will be completed by the patient on the final day of the study as well. Both DM scans taken by the patient on the initial and final days will be accessed by the study coordinator and converted into STL files. The patient will also be asked to take intraoral DM photographs and video scans every 4 days to be uploaded to the DM software.

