- **Subject's participation in study:** Patient will present for regular orthodontic appointments including bonding and adjustments. Upon consenting to participation in the study, an initial iTero scan will be taken in office on day 1. The patient will also take DM scans at home on days 1 and last day (after 5-6 weeks) of the study. The patient will present to the clinic again 5-6 weeks later for a final iTero digital scan taken by the provider, in addition to their regular 5-6 weeks adjustment appointment. A total of two DM scans and two iTero scans will be accumulated for analysis. For the second objective of the study, the patient will take DM scans every 4 days at home for a period this same 5-6 weeks period.
- **Timeline:**
 - IRB approval completed: November 2020
 - Data collection: November 2020 – July 2024
 - Data Analysis and Final Report/Manuscript: July 2024-December 2024
- **Budget:** Patients will not be billed for any additional procedures performed as part of this study. The cost of the orthodontic treatment will be billed to the patient or the patient's insurer, depending on insurance coverage. The same orthodontic procedures will be used for all subjects enrolled in the study and will be equivalent to the standard orthodontic treatment for any orthodontic patient requiring space closure.
- **Dissemination:** The results of this research will be published in a peer-reviewed dental journal. In addition, this work is likely to be presented at national/international meetings.

References:

1. "Telehealth." *World Health Organization*, World Health Organization, 8 Nov. 2019, www.who.int/gho/goe/telehealth/en/. Accessed June 28, 2020.
2. *ADA Policy on Teledentistry*, www.ada.org/en/about-the-ada/ada-positions-policies-and-statements/statement-on-teledentistry use, enhance care and education delivery.

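### The protocol does not settle where the day-1 Dental Monitoring scan is taken, or how either primary scan is ordered against the appliance work, so the accuracy result could mix settings and appliance states

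*Combined protocol and SAP*

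**What the plan says.** Three sections bear on the two primary DM scans.

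- **Study Design, Method of data gathering.** The patient takes DM scans on the first and final days, "while iTero scans are taken by the provider in clinic on these same days". No place is given for the DM scans.
- **Study Procedures, Study Procedure.** On day 1, "the study coordinator will take a digital scan using iTero Element 2 in the clinic the same day if possible". The patient then installs the app and receives the equipment and teaching to "successfully take photo and video scans themselves the same day in the orthodontic clinic". For the last day the text says only "Another DM scan will be completed by the patient on the final day of the study as well".
- **Study Procedures, Subject's participation in study.** "The patient will also take DM scans at home on days 1 and last day". The patient returns to clinic "for a final iTero digital scan taken by the provider, in addition to their regular 5-6 weeks adjustment appointment". The count is fixed: "A total of two DM scans and two iTero scans will be accumulated for analysis".

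Method of measuring accuracy defines the primary measure as the deviation between superimposed STL models built from the two kinds of scan. The primary outcome concerns patient-taken DM scans against provider-taken iTero scans at the maxillary canine. No section asks for the place of a scan, its time, or its order relative to the adjustment to be recorded or used in the analysis.

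**The concern.** Each patient contributes only two DM–iTero pairs to the primary result, so it matters which DM scan forms each pair and under what conditions it was taken.

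There are two separate gaps. The first is setting. A scan taken in clinic just after instruction and one taken unsupervised at home need not have the same error, and the rationale for the study is remote use. If sites of scanning differ between day 1 and the last day, setting is confounded with time.

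The second is appliance state. The final visit includes an adjustment. A DM scan taken at home after that visit could be paired with an iTero scan taken before the adjustment. The accuracy measure is a surface deviation, and the protocol does not say that hardware is masked or removed from the models. A difference in hardware between the paired scans could therefore be counted as DM error.

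**Working it through.** There is no document figure to reproduce: the protocol gives no margin, SD, alpha or power for this comparison. The check is a side-by-side reading, followed by simple arithmetic.

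**Step 1. Place of each primary DM scan**

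| Section | Day-1 DM scan | Last-day DM scan |
|---|---|---|
| Method of data gathering | day only | day only |
| Study Procedure | readable as in clinic, after training | day only |
| Subject's participation in study | at home | at home |

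The conflict over place concerns day 1 only. No section puts the last-day DM scan in clinic.

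**Step 2. Does reading the clinic scan as training remove the conflict?** Only in part. Training in clinic followed by a study scan at home would give two DM scans on day 1, while the protocol counts two DM scans per patient in total for the analysis, one for each of the two days. It does not say that a clinic scan is discarded, or which day-1 scan is converted to STL. Two coordinators could each follow the text and analyse different scans.

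**Step 3. Order at each visit**

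- *Day 1.* The Study Procedure text puts the iTero scan before the DM instruction. It does not say where any appliance work at that visit falls. A home scan on day 1 would come after the visit, because the equipment is handed over there.
- *Last day.* The iTero scan and the adjustment share an appointment, with no order between them. The DM scan is fixed only to the same day, and could come before or after the visit.
- *Both days.* No maximum interval between the paired scans is given.

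**Step 4. What a mix of settings would do.** Let m be the mean DM–iTero deviation for home scans and m − d the mean for clinic scans, with d unknown. If day 1 is in clinic and the last day at home, each setting supplies half of the pairs. That is 20 and 20 pairs if 20 patients are enrolled, or 40 and 40 if 40 are (the protocol states both figures), counting one pair per patient per visit.

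- Pooled mean = (m + (m − d)) / 2 = m − d/2.
- Last day minus day 1 = m − (m − d) = d, plus any true change over time, from which it cannot be separated.
- If both scans are at home, the pooled mean is m and the mix is zero.

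**Step 5. Is same-day tooth movement a problem?** Movement over 12 hours = (rate / 30) × 0.5 day. The rates per 30 days are assumptions, not taken from the documents.

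- 0.5 mm: 0.5/30 × 0.5 = 0.008 mm
- 1 mm: 1/30 × 0.5 = 0.017 mm
- 2 mm: 2/30 × 0.5 = 0.033 mm

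The Introduction cites average absolute differences below 1 mm as sufficient for clinical practice. Against 1 mm, these are 0.8% to 3.3%. Tooth movement between paired scans can be set aside. What remains is setting and hardware, and the documents size neither.

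**The case against.** The strongest reply is that the sections can be read together. The clinic phrase may attach to the teaching rather than to the study scan, and the next sentence gives the patient the devices to take home for collecting data. On that reading both primary scans are home scans and there is no mix. This is a fair reading, but it leaves Step 2 open: no clinic scan is labelled as practice, and the later reference to another DM scan on the final day keeps the ambiguity alive.

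Second, on every reading the patient takes the scan, and the primary outcome is defined by operator rather than place. The Introduction also cites a study that found no significant difference in quality between patient and provider scans. That evidence concerns who scans, not where, and comes from a rapid maxillary expansion model. It does not show that setting is harmless, but nothing in the documents shows that it is harmful either.

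Third, the accuracy measure is paired by day, so a change of setting does not bias either pair for its own setting. This stands. The effect is on the pooled figure and on any contrast between days.

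Fourth, the appliance mechanism is an inference. The protocol does not say what the adjustment changes, or whether brackets, wire and coil lie within the surface compared at the canine. This also stands, and it is why the effect can only be called possible.

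**Conclusion.** The concern holds in a limited form. The place of the day-1 DM scan is inconsistent between two sections, and the order of the two scans and the appliance work is not fixed at either visit. One of the two primary DM scans per patient is therefore affected by the conflict over place, and both by the missing order. The accuracy result could mix clinic and home scans and could pair scans from different appliance states. The consequence of a split by day is d/2 in the pooled mean and d in the contrast between days, with d unknown.

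A reader might infer more than this, in three ways that the documents do not support.

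- That both DM scans have contradictory locations. Only the day-1 scan does.
- That the result does mix settings and appliance states. Following the Subject's participation text throughout gives one setting, and both scans of a pair may happen to fall on the same side of the adjustment.
- That the clinic scan ought to be the primary one. The documents do not require that, and the remote-use rationale gives reason to keep the home scan.

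The correction is worth making because the text as it stands permits a post-adjustment home scan to be compared with a pre-adjustment clinic scan, and preventing that costs almost nothing. It matters also because the pilot is meant to supply preliminary data for a larger study.

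**What to change.** Reconcile Method of data gathering, Study Procedure and Subject's participation in study so that they state one rule.

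1. Name the DM scan that is primary on each day, and use the same setting on both days. If home is chosen, label any in-clinic training scan as not analysed.
2. Require the paired DM and iTero scans to be taken in the same appliance state: both before, or both after, any appliance work at that visit. If home is chosen for day 1, the DM scan follows the visit, so the iTero scan would need to follow any appliance work done there.
3. Record place, time and order relative to the adjustment for each primary scan.
4. For patients already scanned, classify the pairs from records where possible. If they are mixed, report the deviation by setting and by order. Limit the accuracy claim to the setting used, and state how many pairs could not be classified.

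The cost is protocol wording, one data field and slightly tighter visit logistics. No second DM scan per day is needed.

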Canine retraction for space closure after premolar extraction is an excellent model to evaluate rate of tooth movement. Clinical trials with surgical and non-surgical methods of tooth movement acceleration have relied on this tooth movement model to test the efficiency of the different approaches. However, a detailed understanding of the rate of canine retraction and the overall nature of tooth movement is missing in the orthodontic literature. In fact, recently Nickel et al.²⁸ found that canine retraction did not follow the conventional tooth movement phases that have been reported in the literature. Specifically, they reported that a majority of subjects in their study appeared not to have a lag phase and tooth movement appeared to be a continuous process. DM offers a unique opportunity to track the type of tooth movement and magnitude of tooth movement at intervals much shorter than a monthly visit, without the patient needing to visit the provider.

The objective of this study is to test the accuracy of the DM software in determining the precise tooth movements during 5-6 weeks of canine retraction. Furthermore, a description of the magnitude of tooth movement on a biweekly basis will start to provide better information on the nature of the biology of tooth movement. Determining which periods of tooth movement are more significant during the 5-6 weeks of evaluation may help elucidate what the ideal time interval is for patient visits and maximize treatment efficiency. Furthermore, the data could help determine, at an early stage, which patients will be fast and slow movers during orthodontic treatment.

Hypothesis, Aims and Objectives:

- **Null Hypothesis:** There is no significant difference in accuracy of digital scans between the Dental Monitoring and iTero groups in a maxillary canine retraction model.
- **Aims/Objectives**
 - Primary Objective: To evaluate the accuracy and reliability of Dental Monitoring scans to that of iTero digital scans during maxillary canine retraction.
 - Secondary Objective: To quantify the magnitude and type of tooth movement occurring in a 5-6 weeks period in patients undergoing maxillary canine retraction.

Study Design:

- **Study design:** Prospective clinical trial, pilot study
- **Sample size:** 40 patients

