- **Data Safety Monitoring:** The investigator and study coordinators will perform safety monitoring to ensure that risks to subjects are minimal. Serious adverse events associated with routine orthodontic treatment are rare. If any such unanticipated events occur, their provider(s) will provide any necessary clinical/palliative treatment to subjects. An assigned orthodontic resident is always on-call and available to provide such treatment and the study team will be available for consultation. Report of the event will be made to the IRB within 5 days of becoming aware of the occurrence.
- **Additional protections for vulnerable populations:** This study will likely include minors as subjects. As detailed in Form D, additional protections will be taken for this population, including obtaining assent from the subject and permission from a parent/guardian. This study does not involve greater than minimal risk.

➤ **Outcome Variables**

- **Primary Outcome:** There is no significant difference in accuracy or reliability between patient-taken DM scans and provider-taken iTero scans at the maxillary canine.

- **Secondary Outcome:** DM scans allow for precise tracking of tooth movement, which can help optimize treatment. Knowledge gained from this study and future treatment studies regarding the quantity and type of tooth movement occurring in canine retraction cases will allow the provider to be better able to customize subsequent appointments. This will allow for more efficient treatment and potentially reduced treatment time and cost in future patients.

Subject Characteristics: All subjects will have permanent dentition; Ethnicity: N/A; Gender: male and female; Other characteristics: undergoing fixed orthodontic treatment with extraction plan.

➤ Inclusion Criteria

- Male and female
- Patients with fixed orthodontic appliances, in 19x25 SS, using NiTi coil for canine retraction
- Treatment plan requiring extraction of at least one maxillary premolar
- Permanent dentition from first molar to first molar in the maxilla
- Teeth with normal crown morphology
- Fully erupted canines
- Above 11 years of age
- Patients with any cellular phone with a camera

➤ Exclusion Criteria

- Lack of extraction in orthodontic treatment plan
- Previous canine retraction
- Syndromic patients
- Cleft lip/palate patients
- Removable appliances

Recruitment

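### Reliability relative to iTero is in the primary objective and outcome, but it has no definition, method or replicate scans; the planned pairs support DM-iTero agreement only

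*Combined protocol and SAP*

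**What the plan says.** Under *Hypothesis, Aims and Objectives*, the primary objective is "To evaluate the accuracy and reliability of Dental Monitoring scans to that of iTero digital scans during maxillary canine retraction". Under *Outcome Variables*, the primary outcome is worded as a result: "There is no significant difference in accuracy or reliability between patient-taken DM scans and provider-taken iTero scans at the maxillary canine". The null hypothesis is narrower and mentions accuracy alone: "There is no significant difference in accuracy of digital scans between the Dental Monitoring and iTero groups in a maxillary canine retraction model".

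*Study Design* has an entry for measuring accuracy, which superimposes the STL models from the two systems, "assessing the amount of deviation between the 3D models". It has another for measuring tooth movement, which uses the DM Doctor Dashboard. It has none for reliability, and the term is not defined anywhere.

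On scans, *Method of data gathering* has the patient take DM scans on the first and final days, "while iTero scans are taken by the provider in clinic on these same days". *Subject's participation in study* gives the count: "A total of two DM scans and two iTero scans will be accumulated for analysis". The more frequent DM scans have another purpose: "For the second objective of the study, the patient will take DM scans every 4 days at home".

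**The concern.** Accuracy and reliability are listed side by side, so a reader will take them as two properties. In measurement work, reliability normally includes repeatability: how closely a device reproduces its own result when nothing has changed. Showing that two devices are equally repeatable requires an estimate of each device's own error, and that requires something measured more than once in the same state.

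The plan has one scan per device per occasion. A small DM-iTero deviation would be a legitimate finding about agreement. Under the primary outcome as worded, it could be reported as showing no difference in reliability, which these data cannot show directly. The study is a pilot meant to supply preliminary data for a larger one, and publication is planned, so the claim would carry forward.

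**Working it through.** **Inputs.** Two devices, two occasions (day 1 and the final day) and one scan per device per occasion, from *Study Procedure* and *Subject's participation in study*. Number of patients: 40 in the sample size line, 20 in *Method of data gathering*. That conflict is a separate matter, so both are carried here. The plan gives no SD, margin or alpha; results are in units of the SD of the paired differences, at the 95% level.

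**1. The plan's own count.** 2 devices × 2 occasions × 1 scan = 4 scans per patient, that is 2 DM + 2 iTero. This reproduces the stated total.

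**2. Replicate degrees of freedom.** With m scans per device per occasion, each patient contributes 2 × (m − 1) within-occasion degrees of freedom per device. With m = 1 this is 2 × 0 = 0. Over all patients it is 20 × 0 = 0 or 40 × 0 = 0.

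**3. Why the two occasions are not replicates.** The day-1 and final scans are separated by 5-6 weeks of canine retraction. For either device,

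final − day 1 = true movement + (difference of two scan errors).

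True movement is unknown and differs between patients, so this change does not isolate the error.

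**4. What the same-day pairs contain.** Write DM = T + bias + e and iTero = T + f, where T is the true position and e and f are independent errors. Then

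Var(DM − iTero) = Var(e) + Var(f).

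Only the sum is seen. Three assumed pairs of error SDs (DM / iTero, mm) show this:

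- 0.10 / 0.10: √(0.0100 + 0.0100) = 0.141
- 0.14 / 0.02: √(0.0196 + 0.0004) = 0.141
- 0.02 / 0.14: √(0.0004 + 0.0196) = 0.141

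Equal reliability, a much less reliable DM and a much less reliable iTero all give the same spread of differences. Having two occasions repeats the DM-iTero difference, but each difference still carries the sum of both errors.

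**5. What the pairs can deliver.** Taking one value per patient and roughly normal differences:

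- Bias, 95% CI half-width = t(0.975, n − 1)/√n. For n = 20: 2.093/4.472 = 0.468 SD. For n = 40: 2.023/6.325 = 0.320 SD.
- Each 95% limit of agreement, 95% CI half-width = t(0.975, n − 1) × √(1/n + 1.96²/(2(n − 1))). For n = 20: 2.093 × √(0.0500 + 0.1011) = 0.814 SD. For n = 40: 2.023 × √(0.0250 + 0.0493) = 0.551 SD.

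**The case against.** The strongest reply is that reliability here may simply mean consistency between the two methods. The paired scans can supply that, and the defect is then an undefined word. This reading is open and the fix accepts it. But the plan does not state it, and the primary outcome sets reliability beside accuracy as something further.

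A second reply is that the only null hypothesis concerns accuracy and the study is a pilot. A reader might infer that the report is bound to conclude on reliability; the documents do not go that far. What stands is that the primary outcome, as worded, invites that conclusion.

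A third reply is that other planned data could fill the gap.

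- The four-day DM scans do carry DM-only information, since the plan describes "superimposition of teeth from each 3D model created per scan". But they have no iTero counterpart, are taken while the tooth is moving, and belong to the second objective. Nor does the plan designate the photographs and video of one session as replicates.
- Error variances can in theory be split from paired scalar measurements (the Grubbs method). That needs independent errors and equal scaling, which these pairs cannot confirm. It also needs a separate value from each device, and a DM-to-iTero surface deviation does not give one. Canine movement could give one, but *Study Design* measures movement with the DM dashboard only and describes no iTero movement measurement. How well such a split would perform depends on error SDs that the documents do not give.

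**Conclusion.** The point holds. Reliability versus iTero is named in the primary objective and outcome, without a definition or method, and the primary data have 0 replicate degrees of freedom for each device at either stated sample size. Within-device repeatability, and so a comparison of the devices' reliability, cannot be directly estimated. This result comes from counting scans and needs no assumed error size. DM-iTero agreement can be estimated with the precision shown above, assuming one value per patient and approximately normal differences. Good agreement must not be reported as equal reliability.

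A reader might infer that the primary comparison as a whole fails, or that replicate scans must now be added. The documents support neither. The null hypothesis is about accuracy, for which a measure is described and same-day pairs are planned, so the lack of replicates leaves it untouched. Limiting the claim to agreement resolves the problem with the scans already planned.

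**What to change.** - In the primary objective and primary outcome, replace reliability with DM-iTero agreement at the maxillary canine. Alternatively keep the word, define it as inter-method agreement, and state that it is not repeatability.
- Name the compared quantity, using the measure already in *Method of measuring accuracy*: the signed deviation of the same-day superimposed DM and iTero STL models at the canine, one value per patient per occasion. The sign is needed because an absolute deviation cannot show the direction of a bias.
- Report bias and 95% limits of agreement with 95% CIs. The analysis should allow for two occasions per patient, and for two canines where both are used, so that these are not counted as independent patients.
- If DM-iTero differences in canine movement are also reported, state that iTero movement must be derived from the two existing iTero scans, and describe how. The plan does not do so at present.
- Date the change to the primary outcome and disclose it in the report. This version is stamped 12/01/2023 and data collection runs to July 2024, so readers need to know when the change was made relative to the data.

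The cost is a narrower primary claim, a protocol wording amendment and a little more analysis. No scan, visit or replicate is added.
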